4.0 STUDY OBJECTIVES

The PLUM study will collect essential preliminary data to guide and inform a future multi-centered, randomized trial of letrozole versus placebo. The 3 primary study goals are:

1. To assess the feasibility of conducting a randomized, placebo-controlled trial of letrozole for premenopausal women with fibroids.
2. To collect pilot data that examines differences in fibroid symptoms, fibroid volume, and hormone levels among premenopausal women who take letrozole compared with a placebo.

These will be between-group analyses in Months 1 and 2 (Group A vs. Group B) that serve as preliminary data on the efficacy of letrozole in a placebo-controlled trial.

3. To collect pilot data that examines changes in fibroid symptoms, fibroid volume, and hormone levels among premenopausal women taking continuous and intermittent letrozole dosing.

These will be within-group analyses as follows: Months 1-6 for Group A, Months 3-6 for Group B. These data will provide preliminary information on the safety of letrozole use beyond 3 months (Group A) and the rate of fibroid regrowth after letrozole is discontinued (Group B).

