2.0 STUDY RATIONALE

Although there is preliminary evidence to demonstrate a positive effect of AIs on reducing fibroid volume, current studies are insufficient to support widespread clinical use. There are only 2 trials of letrozole monotherapy for fibroids with a total of 56 women; both are open-label, unblinded studies. A randomized, blinded, placebo-controlled trial is needed for an unbiased assessment of letrozole efficacy. In addition, most women with symptomatic fibroids are 35-50 years old and may require many years of treatment until menopause when fibroids regress spontaneously with falling serum estrogen levels. All current AI studies are short-term with only 2-3 months of drug delivery due to lingering concerns that AIs might induce hypoestrogenism among premenopausal women. There are also no studies that evaluate the rate of fibroid regrowth after stopping AIs when fibroid estrogen levels may rapidly rise. If fibroids regrow slowly over several months after stopping AIs, there may be a role for intermittent AI dosing to maximize benefit and minimize harm. Studies are needed to assess the safety profile of letrozole for >3 months of use and to evaluate changes in fibroid volume after letrozole is discontinued.

Our ultimate goal is to conduct a multi-centered, randomized, trial of letrozole versus placebo among women with symptomatic fibroids. This trial will provide gold standard evidence to determine if letrozole results in symptom improvement but offers the advantages of less morbidity and lower rates of recurrence of fibroid symptoms.

To prepare for a future multi-centered randomized trial of letrozole, we will first conduct a controlled pilot study (the PLUM study). The pilot will allow us to assess the feasibility of recruiting and retaining study participants to this drug intervention trial. We will also complete essential preparatory work for a future randomized trial; we will create and test study forms, a manual of operations, and a study database that can be easily adapted for a multi-site trial. The PLUM pilot study will lay the foundation for a successful future study of letrozole as a treatment for uterine fibroids.

The PLUM study will also provide preliminary data on the efficacy of letrozole in treating uterine fibroids. We will use PLUM outcome data to estimate effect sizes and standard deviations to calculate an appropriate sample size for a future randomized trial.

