3.0 STUDY OVERVIEW

This is a randomized, blinded, placebo-controlled trial of oral letrozole among 20 premenopausal women with symptomatic uterine fibroids. Participants will be randomly assigned in a 1:1 ratio to either oral letrozole 2.5mg/day for 6 months (Group A) or intermittent dosing with letrozole 2.5mg/day and an identical placebo capsule (Group B). Group B will receive medication dosing as follows: 2 months of placebo, then 2 months daily letrozole 2.5mg/day, then 2 months of placebo (Table 1). This dosing regimen in the two groups will allow for: 1) between group comparisons in month 1 and 2 to assess the efficacy of letrozole compared with a placebo, 2) within-group comparisons in month 3-6 in group B to evaluate the rate of fibroid regrowth after discontinuing letrozole to evaluate the possibility of intermediate dosing and 3) within-group comparisons in group A in month 1-6 to evaluate the safety of long-term letrozole use. This pilot data will be critical for determining the appropriate long-term dosing regimen in a future, larger, full-scale trial of letrozole.

Month	1	2	3	4	5	6
Group A	L	L	L	L	L	L
Group B	P	P	L	L	P	P

We will assess changes in fibroid symptoms, quality of life, and sexual functioning monthly using standardized, validated questionnaires. In addition, at baseline, month 2, 4 and 6, we will assess changes in the following measures:

- 1) fibroid and uterine volume assessed by pelvic ultrasound
- 2) serum follicle stimulating hormone (FSH) and estradiol levels to determine ovarian function

Study participants will be recruited at UCSF. All study data will be stored securely in a HIPAA compliant, secure database monitored by the UC San Francisco Coordinating Center. A data safety and monitoring board will oversee participant safety and protection.

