10.0 STATISTICAL CONSIDERATIONS

Data analysis plan: We will use descriptive statistics to characterize the feasibility and process measures listed in Table 5, with 95% confidence intervals. Changes in UFS-QOL scores, the primary outcome, as well as secondary outcomes including hormone levels and fibroid volume, will be compared using linear mixed models for repeated measures, adjusting for baseline. We will estimate 1) between-group differences in change from baseline to months 1 and 2; 2) changes from baseline to months 1-3 and 4-6 in group A; and 3) changes from month 3 to months 5 and 6 within group B.

Sample size calculations: This is a pilot study with the aim of assessing the feasibility of implementing a definitive letrozole trial. Therefore, we chose a sample size that would be large enough to assess feasibility, but small enough to complete the pilot within a the1 year timeframe and with a limited budget. Accordingly, the study will not have power to detect small treatment effects. In the PROMISe pilot study discussed in Preliminary Studies, the standard deviation of the UFS-QOL SSS was 20, and correlation of baseline with follow-up scores declined from 0.5 at 1 month to nearly zero at 3 months. In the analysis for AIM 2 of between-group differences in the change in UFS-QOL from baseline to 2 months , the sample size of 20 will provide 80% power to detect a between-group difference of 13.4 points in average SSS scores at months 1 and 2, after accounting for short term attrition of 10%. In the analysis for AIM 3, assessing longer term changes in SSS scores within group A, the sample of 15 women have 80% power to detect average changes from baseline to months 1-3 and 4-6 of 16.0 points. In additional analysis for AIM 3, assessing changes from month 3 to months 5-6 in group B, the corresponding minimum detectable effect will be 18 points. Effects of this magnitude are

clinically relevant because 15-20 points is the mean difference in SSS between women with symptomatic fibroids and women without fibroids.

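### The Group B regrowth contrast in Section 10.0 uses months with no fibroid volume or hormone data; secondarily, no estimate uses the randomised difference between arms in months 5-6.

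*Combined protocol and SAP*

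**What the plan says.** Section 3.0 gives Group B the regrowth question, through "within-group comparisons in month 3-6 in group B to evaluate the rate of fibroid regrowth after discontinuing letrozole". Section 4.0 keeps the third aim inside each arm: "These will be within-group analyses as follows: Months 1-6 for Group A, Months 3-6 for Group B".

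Section 10.0 covers the primary UFS-QOL outcome, and its "secondary outcomes including hormone levels and fibroid volume, will be compared using linear mixed models for repeated measures, adjusting for baseline". It then lists three estimates for all of these outcomes together:

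1. "between-group differences in change from baseline to months 1 and 2";
2. "2) changes from baseline to months 1-3 and 4-6 in group A";
3. "changes from month 3 to months 5 and 6 within group B".

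No separate list is given for volume or hormones.

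The measurement schedule is in Sections 3.0, 6.1.B, 6.1.C and Table 2 (Section 6.1.G). Symptom questionnaires are monthly. Ultrasound, estradiol and FSH are taken at baseline and at the end of months 2, 4 and 6.

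Table 1 (Section 3.0) has Group A on letrozole throughout. Group B is on placebo in months 1-2, letrozole in months 3-4 and placebo in months 5-6.

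**The concern.** The third estimate is the plan's only listed measure of what happens after letrozole stops, and for fibroid volume two of its three months are never observed. Section 2.0 explains why that matters: "If fibroids regrow slowly over several months after stopping AIs, there may be a role for intermittent AI dosing". Section 3.0 adds: "This pilot data will be critical for determining the appropriate long-term dosing regimen in a future, larger, full-scale trial of letrozole". A regrowth estimate that has to be redefined after the data are in is a weak basis for that use, and the choice could look data-driven.

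The second matter is smaller. A change measured inside Group B contains any time trend that both arms share as well as the effect of the regimen. Group A's change from baseline is also open to regression to the mean, since women enter because they have symptoms. The arms receive different treatment in months 5-6 and the data are already scheduled, but Sections 3.0, 4.0 and 10.0 compare them only in months 1 and 2.

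**Working it through.** **Months needed against months measured (volume, estradiol, FSH)**

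| Listed estimate | Months needed | Months with data |
|---|---|---|
| A versus B | baseline; 1, 2 | baseline; 2 |
| Within A | baseline; 1-3; 4-6 | baseline; 2; 4, 6 |
| Within B | 3; 5, 6 | none; 6 |

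The first two keep their starting point and at least one month in each window, so they survive in reduced form. The third loses its starting point. Month 4 and month 6 are both measured, and they bracket Group B's second placebo period. For UFS-QOL, months 3, 4, 5 and 6 all exist. Month 3 falls inside Group B's letrozole period, so a month-3 start mixes further time on drug with time off it. Month 4 does not.

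**The plan's own figure for this contrast**

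Section 10.0 gives 18 points at 80% power, for UFS-QOL SSS only. Inputs from Section 10.0: SD 20, and baseline to follow-up correlation 0.5 at 1 month and nearly 0 at 3 months. Assumed: two-sided 5% level, and correlations between follow-up months of 0.5, 0.25 and 0 at lags 1, 2 and 3.

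- Variance of (months 5-6 mean minus month 3) = 400 + 400(1 + 0.5)/2 - 400(0.25 + 0) = 600; SD 24.5.
- Detectable change = 2.80 x 24.5/sqrt(n) = 21.7 at n = 10 and 17.7 at n = 15.

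So 18 is approached at 15 women but not at the 10 that 1:1 allocation of 20 gives. This depends on the assumed correlations, and the point does not rest on it. With the same assumptions, a month-4 start has variance 400 + 300 - 400(0.5 + 0.25) = 400, SD 20. At 9 women the SE is 6.7, against 8.2 for the month-3 start.

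**Volume and hormones, in SD units**

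The documents give no SD. With an assumed 9 women per arm and month 4-6 correlation r:

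| Estimate | Formula | r = 0 | 0.5 | 0.8 |
|---|---|---|---|---|
| Within-B change, month 4 to 6 | sqrt(2(1-r)/9) | 0.47 | 0.33 | 0.21 |
| A-minus-B difference in that change | sqrt(4(1-r)/9) | 0.67 | 0.47 | 0.30 |
| A minus B at month 6, before baseline adjustment | sqrt(2/9) | 0.47 | 0.47 | 0.47 |

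**A minus B in UFS-QOL SSS, months 5-6**

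A trend of d points shared by both arms adds d to Group B's change and 0 to A minus B. The documents give no d.

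Precision uses SD 20 and an assumed 9 per arm (10% attrition, which Section 10.0 states for the short term only). No gain is taken from baseline adjustment, because the stated correlation is nearly zero by 3 months. With month 5-6 correlation r, SE of the difference in two-month means = sqrt(2 x 200(1 + r)/9). The t value on 16 df is 2.12, and power is from the noncentral t.

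| Estimate | SE | 95% CI half-width | Power at 15 points |
|---|---|---|---|
| Mean of months 5-6, r = 0 | 6.7 | 14 | 56% |
| Mean, r = 0.5 | 8.2 | 17 | 41% |
| Mean, r = 0.7 | 8.7 | 18 | 37% |
| Single month | sqrt(2 x 400/9) = 9.4 | 20 | 32% |

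**Precision relative to the within-B month 3 to months 5-6 contrast**

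If all follow-up correlations equal r, the within-B SE is sqrt(600(1 - r)/9), which is 8.2, 5.8 and 4.5 at r = 0, 0.5 and 0.7. The ratio of the A-minus-B SE to it is 0.82, 1.41 and 1.94.

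**The case against.** *The model can fill the gap.* A mixed model with a linear time trend could return a month-3 volume. It would do so by assuming a smooth course through the switches of treatment at the ends of months 2 and 4, which is the behaviour under study. With month as a category, no estimate exists. This objection does not stand.

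*It is only wording.* Largely true. A reader might infer that fibroid regrowth cannot be measured in this trial, or that Section 4.0 is itself in error. Neither follows. Month 4 and month 6 volumes are scheduled, and a Group B window of months 3-6 is compatible with using them. The defect lies in the list in Section 10.0, and it does not touch UFS-QOL, which is collected monthly.

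*The missing A-versus-B estimate is an omission by design.* Much of this stands. This is a 20-woman pilot sized for feasibility, and its third aim promises preliminary within-group information on safety and regrowth rate. A regrowth rate is a within-woman quantity, and A minus B in months 5-6 does not supply one. A reader might infer that the within-group results are biased. The documents do not show that: they give no size for a shared trend, and eligibility sets no UFS-QOL cut-off from which regression to the mean could be sized. Nor would A minus B be a pure effect of stopping, because by the end of month 4 Group A has had 4 months of letrozole and Group B 2.

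**Conclusion.** The main point holds on the text alone and rests on no assumption: for fibroid volume, estradiol and FSH, the listed Group B contrast has data at 1 of its 3 months, and its starting month is never observed. It should be corrected before analysis.

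The A-minus-B estimate in months 5-6 is a worthwhile, inexpensive addition, and its absence is not an error. Its value is that randomisation protects it from a shared trend of unknown size. Its cost is imprecision. The half-widths of 14 to 18 points for the months 5-6 mean, and 20 for a single month, are as large as or comparable with the 15-20 points that Section 10.0 treats as clinically relevant. Those figures rest on SD 20, an assumed 9 per arm carried to month 6, and an unstated month 5-6 correlation. Whether it is more or less precise than the within-B contrast depends on follow-up correlations that the documents do not give, so no fixed penalty can be quoted. It suits estimation, not testing.

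**What to change.** In Section 10.0:

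1. For volume, estradiol and FSH, replace the Group B contrast with the within-B change from month 4 to month 6.
2. For UFS-QOL, add the within-B change from month 4 to months 5 and 6, so that all outcomes share the end-of-letrozole starting point.
3. As exploratory estimates with 95% CIs, from the planned mixed model with group-by-month terms, add the baseline-adjusted A-minus-B difference in the months 5-6 mean of UFS-QOL, and at month 6 for volume, estradiol and FSH. Give the A-minus-B difference in the month 4 to 6 change as supporting.
4. Label item 3 a randomised comparison of continuous with intermittent regimens, not a withdrawal effect or a regrowth rate. Keep the within-group changes.

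This needs no new visits, tests or participants and leaves dosing unchanged. The price is a few more contrasts in a small trial and wide intervals. The supporting difference in change has an SE sqrt(2) = 1.41 times that of the within-B month 4 to 6 change at equal arm sizes, so item 1 remains the regrowth estimate.

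### Group B's own change on moving from placebo to letrozole is not a planned estimate, so a small off-drug change could mean lasting benefit or no benefit to lose

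*Combined protocol and SAP*

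**What the plan says.** Section 3.0 gives Group B "2 months of placebo, then 2 months daily letrozole 2.5mg/day, then 2 months of placebo". It states the purpose of the within-group work as "within-group comparisons in month 3-6 in group B to evaluate the rate of fibroid regrowth after discontinuing letrozole", and says that the pilot will inform the long-term regimen of a larger trial. Section 2.0 explains why regrowth matters: "If fibroids regrow slowly over several months after stopping AIs, there may be a role for intermittent AI dosing".

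Goal 3 in section 4.0 reads: "These will be within-group analyses as follows: Months 1-6 for Group A, Months 3-6 for Group B". Taken alone, that line could cover the on-letrozole months 3 and 4. Section 10.0 is more specific. Outcomes "will be compared using linear mixed models for repeated measures, adjusting for baseline", and three sets of estimates follow: "between-group differences in change from baseline to months 1 and 2; 2) changes from baseline to months 1-3 and 4-6 in group A", and then "changes from month 3 to months 5 and 6 within group B".

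Under section 6.1, ultrasound and hormones are measured at baseline and at the end of months 2, 4 and 6. Symptom questionnaires are completed at baseline and every month.

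**The concern.** Group B is the only arm in which letrozole is stopped while follow-up of volume and symptoms continues, so it carries the question of intermittent dosing. Its one within-group contrast starts at month 3, a month after letrozole begins. By section 1.0's account, 90% of the volume reduction in earlier letrozole trials had occurred within one month. If symptoms follow a similar course, most of the response is over before the contrast begins.

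What happens off drug has to be read against what happened on drug in the same women. If Group B improved and then changed little, the benefit lasted. If it never improved, there was nothing to lose, and the off-drug change is also small. These two results point in different directions for intermittent dosing, and the listed estimates do not separate them. Section 2.0 also wants effect sizes and standard deviations for a later trial, yet half of the women who start letrozole contribute no planned estimate of on-drug change.

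**Working it through.** **1. The plan's own figure for Group B.** Section 10.0 gives a minimum detectable change of 18 points from month 3 to months 5-6.
- Inputs from section 10.0: SD 20; correlation with baseline 0.5 at one month and near zero at three; 80% power.
- Assumptions: two-sided 5% level (not stated); 0.25 at two months, by interpolation; the same correlation for every pair of months at the same lag.
- Variance of (mean of months 5 and 6) − (month 3) = 400 × (1 + 0.25 + 0.25 + 2×0.25×0.5 − 2×0.5×0.25 − 2×0.5×0) = 600.
- With 15 women: SE = √(600/15) = 6.32; detectable change = (1.96 + 0.84) × 6.32 = 17.7, close to 18.
- With the 10 women that 1:1 allocation of 20 gives: SE = 7.75; detectable change 21.7. Other correlations can bring this near 18, so the figure is neither confirmed nor refuted. The statement of 15 women in one group must be reconciled with 20 randomised 1:1, but the present point does not depend on it.

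**2. Contrasts against the design.**

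| Transition | Planned estimate |
|---|---|
| A on letrozole v. B on placebo, months 1 and 2 | yes, between groups |
| A from baseline, on letrozole throughout | yes |
| B from placebo (month 2) to letrozole (month 4) | none |
| B from letrozole to placebo | yes, from month 3 |

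For volume and hormones there is no measurement at month 3 or 5, so the off-drug change can only be month 4 to month 6. That is used below.

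**3. One woman.** Set month-2 volume to 100. Section 1.0 reports 45-46% shrinkage after three months of letrozole; 45% at two months is assumed. A responder who keeps all her benefit goes 100, 55, 55. A non-responder goes 100, 100, 100. Both show an off-drug change of zero.

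**4. The group mean.** Mean rise from month 4 to 6 = (responder share) × 45 × (share of the loss regained). The responder and regained shares are illustrative.

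| Responders | Regained by responders | Mean fall, months 2-4 | Mean rise, months 4-6 | Rise ÷ fall |
|---|---|---|---|---|
| 100% | 25% | 45 | 11.25 | 25% |
| 50% | 50% | 22.5 | 11.25 | 50% |
| 25% | 100% | 11.25 | 11.25 | 100% |

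The rise alone cannot tell these apart. The month 2-4 fall can.

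**5. Sensitivity to the size of response.** With on-drug shrinkage r and off-drug growth g relative to the month-4 volume, the share regained is g(1−r)/r. Take g = 10% (assumed). Over section 1.0's 35-55% for aromatase inhibitors, the share runs from 0.10×0.65/0.35 = 18.6% to 0.10×0.45/0.55 = 8.2%. At r = 20% or 10%, both assumed and outside that range, it is 40% or 90%.

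**6. Precision of the added contrast for UFS-QOL**, under the assumptions in step 1.
- Mean of months 3-4 minus mean of months 1-2: variance = 400 × [1 + 2×(0.125 + 0.125 − 0.0625 − 0.0625 − 0.125)] = 400. With n = 10: SE = √40 = 6.32; 95% half-width = 2.262 × 6.32 = 14.3 points. With n = 9 (10% attrition): 15.4.
- Month 2 to month 4 alone: variance = 400 × (2 − 2×0.25) = 600. With n = 10: half-width = 2.262 × 7.75 = 17.5 points.
- No SD is given for volume, so its precision cannot be calculated.

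**The case against.** The strongest reply is that the randomised comparison at months 1 and 2 already estimates the two-month effect of letrozole. Because allocation is random, it also estimates the response to be expected in Group B. If letrozole does nothing, this is where it should show. That stands. A reader might infer that the regrowth result has no reference at all; the documents do not support that. What is missing is narrower: whether the roughly 10 Group B women themselves responded before withdrawal.

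A reader might also infer that the decision on intermittent dosing would be reversed. The documents do not support that either. Section 2.0 states a conditional rationale, not a decision rule, and nothing classifies individual women as slow to regrow. Over the documented 35-55% shrinkage the regained share stays between about 8% and 19% in step 5. The larger shares need weaker responses that are assumptions.

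Two tempting remedies also fail. A per-woman regained share is unstable where it matters most. For a woman with no true change and independent, equal normal measurement errors, (e6 − e4)/(e2 − e4) follows a Cauchy distribution centred at 0.5: its median says half was regained, and it has no mean. Nor is Group A's month 2-4 change a clean time control, since Group A takes letrozole throughout.

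Finally, the data are collected, the absolute off-drug change can be estimated, and this is a 20-woman feasibility pilot. All true. But the quantity needed to read the arm's main result should be named in advance, not chosen afterwards.

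**Conclusion.** The point holds as an omission from the list of planned estimates, not as a gap in data collection. Section 10.0 never estimates Group B's change on starting letrozole, and the between-group contrast supplies it only indirectly. A small off-drug change therefore has two readings that the listed estimates cannot separate, which limits what this arm can say about intermittent dosing.

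The ambiguity itself follows from the design and needs no assumed figures. Its size does depend on them: the example with one 11.25-point rise and three different regained shares assumes 45% shrinkage in responders at two months and illustrative responder shares. The added UFS-QOL estimate will be imprecise, about ±14 points with 10 women, given SD 20 and lag correlations of 0.5, 0.25 and 0. It is also an uncontrolled before-and-after change, and should be read as one.

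**What to change.** In section 10.0, add a Group B contrast from the planned mixed model:
- month 2 to month 4 for fibroid volume, estradiol and FSH;
- mean of months 1-2 to mean of months 3-4 for UFS-QOL.

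Report it with a 95% confidence interval beside the off-drug change, on the same scale, and plot each woman's values at baseline and months 2, 4 and 6. For volume and hormones, state the off-drug change as month 4 to month 6, the only one the visit schedule allows.

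If a regained share is reported, give it at group level only: mean off-drug rise divided by mean month 2-4 fall, with an interval. Do not report per-woman ratios. Group A's month 2-4 change may be shown for context, with a note that Group A is on letrozole throughout. Align the goal 3 wording in section 4.0.

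The cost is a few lines of text and a small amount of analysis. No visit, measurement or participant is added. The price is a wide interval, to be presented as estimation and not as a test.
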